9.8. Quality control

All surveys are programmed internally using Redacted Decipher system, a secure online data collection software. Redacted guarantees senior-level programming support on all research engagements, with programmers who have been trained using a stringent quality control

process to ensure that the surveys are programmed error-free. Redacted utilizes a rigorous quality assurance process which includes the following:

- Programmer and researcher manual testing: Manual testing process which includes several members of the research and programming team (Operations) testing each survey path thoroughly to ensure accuracy in both the text and all survey logic (skip and jump patterns). Each survey is tested on stimulator associated with the web browsers.
- Random Data Generation (RDG) and Data Check Edits (DCE): Once testing is completed by both the operations and research teams, a member of the operations team runs a set of randomly generated data ("dummy" data) to fill all possible paths and quotas, then writes a programmatic check designed to test the validity of the survey. Each question is tested for the correct number and coding of responses, that respondents answering the questions meet the base criteria as well as duplicate any calculated or algorithmic variables and compared for accuracy. An independent member of the operations team then writes the DCE. The data is also run through the DCE one again with soft launch data, full field data (data from the day after full fielding has begun) and the final data set.
- Soft launching: Once the DCE is approved, begins fielding with a limited amount of sample designed to recruit 10% of the total quota. The soft launch data is then thoroughly checked utilizing the DCE to ensure programming accuracy.
- In-field data checks: A core member of the research team monitors the data at regular intervals (e.g., 10%, 25%, 50%, 75% of data collection). The data is examined for the following, and considered together to identify and exclude respondents for whom the data is suspect/of poor quality:
 - Length of survey survey length is estimated prior to fielding; any surveys completed substantially below a lower threshold are flagged with the help of hidden variables.
 - O Quality control questions each survey includes a few questions for the sole purpose of being a quality control check (e.g., "For quality control purposes, please select No" with response options of "Yes, No, Maybe"). These questions help to evaluate a respondent's level of attention to the survey.

Standard organizational procedures will be followed to ensure data quality and integrity, including data collection, archiving of statistical programs, appropriate documentation of data cleaning, validity for variables and description of data.

9.9. Strengths and Limitations of the Research Methods

9.9.1. Strengths

1. Web-based surveys

Redacted

Web-based surveys have been selected as the preferred research approach because:

- The HCP survey includes behavioral scenario-based questions that might be difficult to implement using other approaches.
- Web-based surveys can be answered at the participant's convenience so that an interview does not need arranging this can increase a participant's motivation to do the survey (improving response rates), thus resulting in more consistent completion of surveys.
- Web-based surveys are programmed to ask standardized questions and should elicit more consistent and reliable results than questions asked by telephone interviewers.
- Web-based techniques allow for a degree of interactivity to be introduced into the survey (e.g., logic to ask follow-on questions or not ask irrelevant questions), which strengthens the validity of the behavioral scenarios.
- 2. Questionnaire design and testing
- The web questionnaires include general questions followed by specific ones. They include both open and closed questions. As the HCPs may understand the right answer in subsequent questions, it will not be possible to go back in the questionnaire and edit answers in former questions.
- The questionnaires will be tested for their clarity. It will also be checked whether there are questions which would suggest a specific answer for any reason.
- 3. Experience in drug safety and the evaluation of RM measures

The study will be conducted by an experienced team specialized in the design and conduct of such surveys. It follows SOPs, as well as the methodological guidelines from SFDA Guideline on GVP.

4. Quality control and compliance

Quality controls are implemented on a regular basis by our teams.

9.9.2. Limitations

1. Bias

Selection bias

a) HCPs survey

The potential for selection bias of HCPs participating in a survey is an inherent limitation to any study based on volunteer participation. For instance, it is possible that HCPs willing to

participate in the study will have the highest awareness of risks associated with use of voriconazole.

Non-response bias may also be introduced into the study if targeted HCPs have activated filters in their mailbox that block spam and unsolicited emails. If a very strict degree of message filtering is set, they may not even see the invitation to participate in the survey. Having multiple email addresses could also be a critical situation. If the one used is not the primary address or if the HCPs do not check their emails frequently, they will not receive the invitation during the recruitment period. Some HCPs who are sent a letter may not receive it. This is one of the reasons why the HCPs will also be contacted by phone.

Selection and non-response bias will be assessed by comparing select characteristics between survey non-responders and responders using descriptive statistics, and will be included in the final study report.

Information bias

Recall bias may lead to an underestimation of the HCP recalling having received aRMMs. To mitigate the risk of recall bias for HCPs, they will be recruited in the survey if they have provided (prescribed or dispensed) voriconazole in the past 12 months.

Moreover, web surveys may promote social desirability bias, which refers to the tendency of HCP to give socially desirable/expected responses instead of choosing those reflecting their current knowledge or behavior, e.g., physicians can copy-paste information gathered online instead of giving their own opinions. Social desirability can affect the validity of survey research findings, but the use of prepopulated items in the questionnaire could/tends to reduce this bias. The access to the web questionnaire interface will be strictly limited to the invited participants, with the possibility to participate only once, and a traceability system. Thus, stakeholder bias (multiple answers of people who have a personal interest in survey results and/or who incite peers to fulfill the survey in order to influence the results) or unverified respondents (when it is not possible to verify who responds) are not applicable.

All questions must be answered in order to complete the survey. In each survey, response options presented in a list will be presented in random order (where appropriate) to minimise positional bias. Programming will be reviewed by quality control and simulated users (User Acceptance Testing) prior to implementing the survey.

2. Generalization of the survey results to the overall target population

In such surveys, the generalization and external validity of the results is restricted to HCPs who can be reached and are willing (and able) to answer a questionnaire online questionnaire. These HCPs may not be fully representative of the whole target population.

The study report will discuss the results in the light of the limitations described above including variability and uncertainty of the data and methods.

Redacted

Finally, the marketing authorization holder (MAH) acknowledges that an a priori threshold of 80% correct per risk questions will be used to define the success of the program. However as acknowledged by EMA, the selection of this threshold for success is subjective (7 May 2015 PRAC Rapporteur PASS Protocol Assessment Report; Procedure no.: EMEA/H/C/000387/MEA 087.2) and not based on a prior knowledge, experience, or established scientific criteria in the education or risk communication literature. The MAH expects that the knowledge may differ by key risk message, clinical practice, & HCP specialties. Moreover, sample size may not be sufficient to conduct subgroup or stratified analyses.

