9.2. Setting

The target population will include all HCPs who were targeted to receive Vfend® aRMM materials within 12 months preceding the survey.

At the time of protocol writing, approximately to HCPs were prescribing/dispensing voriconazole in Saudi Arabia and around of these targeted to receive the RM tools in-person, per Pfizer Inc.'s Distribution List. Given this relatively small pool of HCPs, an empirical sample size of 10 HCPs is proposed.

HCPs recruitment and survey will be conducted by the following process:

- HCPs will be invited to participate in the survey by email and/or phone. An email
 invitation will include a web link directing to a webtool named 'Decipher', where the
 survey questionnaire will be available. In the invitation, the survey background and
 objectives, the contact information for questions will be explained to the HCPs.
 Instructions detailing the survey requirements will be displayed at the start of the
 survey.
- If the HCPs agree to participate in the survey, they can access the survey and the instructions for the web questionnaire by clicking on the email link.
- If the questionnaire is not completed in the first attempt, HCPs will receive a reminder email and/or phone (first reminder) 1 week after the initial invitation.
- If the web questionnare remains incomplete, a second reminder will be sent about 2 weeks after the initial invitation.
- If the questionnaire still remains incomplete, a third (and final) reminder will be sent 3 weeks after the initial invitation.

An HCP will be considered unreachable if he/she has been contacted up to 3 times without an answer. For each recruited HCP, the number of times the HCP is contacted, as well as the date and time when he/she completes the web questionnaire, will be recorded. HCP recruitment will be competitive.

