- Knowledge/ comprehension of the risks of phototoxicity, SCC of the skin and hepatic toxicity. Q7 and Q8

• Practice-related questions and self-declared behavior with respect to mitigating the risks, as described in the SPC. Q18, Q18a, Q19, Q20, Q21, and Q22

The key messages informing HCPs about the risks of phototoxicity, SCC of the skin and hepatic toxicity with voriconazole, and instructions on how to manage these risks when treating patients with voriconazole have been identified from the most current version of the SPC¹ and will be used for evaluation of the HCP's knowledge.

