9.4.1. Data Collection Process

Eligible HCPs (those HCPs to whom the RM tools were distributed by hand) will receive a letter by E-mail inviting them to participate in the survey. The invitation letter will include: an overview of the rationale for the survey, reminder about the educational materials, the secure URL to be copied and pasted into their browser, and a unique user identifier (ID). The survey data collection will be open until 10 completed surveys are received, up to 60-90 days. The survey start date begins within 12-18 months after initiation of distribution (05 February 2023) of the aRMMs tools in the Saudi Arabia.

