Annex 1.2. HCP Survey Questionnaire

SURVEY LEGEND

- **[PROGRAMMER]** is used to indicate directions to the programmer and is set in bold, red, uppercase letters between square brackets.
- [BEGIN SURVEY CONTENT] and [END SURVEY CONTENT] are used to indicate to the programmer the type of survey administration and the beginning and end of the survey.
- **[TERMINATE]** is displayed next to responses that should cause the survey to end. The following termination language will be programmed into the survey or read by the interviewer.
 - Thank you for your time today. Based on your answer, you are not eligible to take part in this survey.
- **[GO TO Qx]** (skip logic) is inserted after a response to indicate to the programmer that the survey should skip to the indicated question (for example, **[GO TO Q17]** skips to question 17). If no skip logic is indicated the survey continues to the next question in the sequence.
- **[FREE TEXT]** indicates to the programmer that one line should be provided for data entry.
- [MULTILINE INPUT] indicates to the programmer that multiple lines should be provided for data entry (for example, two address lines).

[PREAMBLE 2]

VFEND® (voriconazole) Healthcare Professional (HCP) Survey

Please provide a response to all questions and statements.

1. Do you agree to take part in this survey?

□ Yes

		No [TERMINATE]
2.	Have mont	e you managed patient(s) treated with VFEND (voriconazole) within the past 12 ths?
		Yes
		No [TERMINATE]
3.		you currently employed by Pfizer Saudi Limited or United BioSource oration?
		Yes [TERMINATE]
		No
4.		you ever participated in qualitative research of the VFEND (voriconazole) Minimisation materials?
		Yes [TERMINATE]
		No
5.	Wha	t is your primary medical specialty?
		Critical Care
		Haematology
		Infectious diseases
		Intensive Care
		Microbiology
		Oncology
		Solid Organ Transplant
		Clinical pharmacist
		Non-clinical pharmacist
		Other Subspecialty: (Specify) [FREE TEXT]

		Other: (Specify) [FREE TEXT]
5a.	Whe	ere do you practice as an HCP?
		Dahran
		Dammam
		Hail
		Jeddah
		Jubail
		Khamis Mushait
		Khobar
		Madinah
		Makkah
		Najran
		Qurayat
		Riyadh
		Tabuk
		Taif
		Other: (Specify) [FREE TEXT]
6.	For	how long have you been practicing as an HCP?
		≤5 years
		6-15 years
		>15 years

7. According to the SPC/PI, the known risks for VFEND (voriconazole) are as follows: (Please select only one response for each of the risks listed in the table below.)

	Yes	No	I Don't Know

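### Prepopulated items do not stop HCPs looking up the answers to Q7 and Q8, so the knowledge result (objective 3) may be biased upward by an unknown amount

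*Protocol*

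**What the plan says.** Under information bias, Protocol section 9.9.2 warns that web surveys may draw expected answers rather than ones reflecting the respondent's current knowledge or behaviour. Its example is that "physicians can copy-paste information gathered online instead of giving their own opinions". The mitigation it gives is that "the use of prepopulated items in the questionnaire could/tends to reduce this bias".

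Other parts of the protocol that bear on this:

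- **Items.** In Annex 1.2, Q7 lists six possible risks (yes, no, don't know) and Q8 lists five statements (true, false, don't know). The Q7 stem begins "According to the SPC/PI, the known risks for VFEND (voriconazole) are as follows".
- **Key.** Section 9.4 says the key risk messages "have been identified from the most current version of the SPC¹ and will be used for evaluation of the HCP's knowledge".
- **Setting.** The questionnaire is self-administered online. Section 9.9.1 gives as a strength that "Web-based surveys can be answered at the participant's convenience". Under section 9.4.1 the invitation carries a "reminder about the educational materials".
- **Timing check.** Section 9.8 says that "any surveys completed substantially below a lower threshold are flagged". No upper limit is stated.
- **Success rule.** Annex 1.5 counts an HCP as successful for knowledge with at least 9 of 11 correct, and the programme as successful if at least 80% of HCPs are. Section 9.5 aims for 10 completed surveys and says the 80% criterion will not be formally tested.

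**The concern.** Objective 3 is about what HCPs know. If some of them consult the SPC or the RM tools while answering, the score measures their access to the source as well as their knowledge. The key is taken from the SPC, so accurate look-up moves answers towards it and the distortion runs in one direction.

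The protocol names the threat, but its mitigation does not reach the route that closed questions leave open. At stake is the reading of a favourable knowledge result: the criterion could be met partly by HCPs who did not hold the information unaided, and no control described would show it.

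**Working it through.** **Step 1. Set each stated control against look-up.**

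| Control | Section | What it does | Limits or detects look-up? |
|---|---|---|---|
| Prepopulated items | 9.9.2 | Removes pasted text | No |
| No going back to edit answers | 9.9.1 | Stops later questions informing earlier ones | No, outside sources stay open |
| Flag on survey length | 9.8 | Flags surveys that are too short | No, look-up lengthens a survey |
| Attention-check questions | 9.8 | Measures attention | No |
| Restricted, single access | 9.9.2 | Prevents duplicate or unverified respondents | No |

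Q7 carries 6 of the 11 knowledge points and points to the SPC. Q8 carries the other 5; it does not name the SPC but can be checked in the same way.

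**Step 2. Reproduce the plan's cut-offs.** 9/11 = 81.8%, and 0.8 × 11 = 8.8, which rounds up to 9, so the HCP-level rule agrees with its description as about 80%. With 10 HCPs, at least 80% means at least 8. The exact 95% confidence interval for 8/10 is 44.4% to 97.5%. The sample size is declared empirical, so there is no power figure to reproduce.

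**Step 3. Illustrate the effect.** Let h be the proportion of HCPs who would pass unaided and L the share who look answers up. Neither is in the documents. Assume that an HCP who looks answers up always passes, that look-up is unrelated to unaided knowledge, and that all 10 surveys are completed. Then

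observed pass rate q = h + (1 − h) × L

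and the chance of meeting the criterion is P(X ≥ 8) for X ~ Binomial(10, q).

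For h = 0.60 and L = 0.25: q = 0.60 + 0.40 × 0.25 = 0.70.

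- At q = 0.60: P(X ≥ 8) = 0.167.
- At q = 0.70: P(X ≥ 8) = 0.383.

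Over a range of assumed values:

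| Unaided pass rate h | L | Observed rate q | P(X ≥ 8) |
|---|---|---|---|
| 0.60 | 0 | 0.60 | 0.17 |
| 0.60 | 0.10 | 0.64 | 0.24 |
| 0.60 | 0.25 | 0.70 | 0.38 |
| 0.60 | 0.50 | 0.80 | 0.68 |
| 0.70 | 0 | 0.70 | 0.38 |
| 0.70 | 0.10 | 0.73 | 0.47 |
| 0.70 | 0.50 | 0.85 | 0.82 |

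At L = 0 there is no bias. At h = 0.60 the pass rate rises by 4 percentage points when L = 0.10 and by 20 when L = 0.50.

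**The case against.** Much of the case on the other side is fair.

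- **The claim in 9.9.2 is modest.** It concerns social desirability in general, uses online copying as one example, and is hedged. Closed items do remove pasted text. This stands: the sentence is incomplete rather than false, and there is no ground for deleting it.
- **An instruction to answer unaided may exist.** A reader might infer that HCPs are never asked to answer from their own knowledge. The documents do not support that. Section 9.2 says instructions appear at the start of the survey, and neither the preamble text nor the invitation letter is shown. It can be said only that the visible Q7 and Q8 stems carry no such request.
- **Pausing and resuming is not described.** Section 9.2 says "If the questionnaire is not completed in the first attempt, HCPs will receive a reminder email". A reader might infer that an HCP can stop at Q7, consult the SPC and return later, but no save-and-resume function is stated. The point does not need it, because one unsupervised, self-paced sitting is enough.
- **Naming the SPC in Q7 has a purpose.** It tells respondents which standard defines a known risk and keeps the distractor items unambiguous. This stands, and the reference should be kept.
- **Some detection may be possible.** Survey length is captured and completion times are recorded, and the SAP or data-check specification could add rules. That is possible, but the only timing direction stated here is too short, and whole-survey length does not isolate Q7 and Q8.
- **The threshold is subjective, untested and disclosed as such.** Sections 9.7 and 9.9.2 also promise to discuss results in context. True, but the 80% criterion still defines programme success, and nothing described would supply data on look-up for that discussion.

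**Conclusion.** The point holds in a limited form. The stated mitigation does not address look-up, and no other control described limits or detects it. The knowledge result may therefore be an upper estimate.

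The direction rests on the key following the SPC, as section 9.4 indicates, and on look-up being accurate. The size cannot be estimated from the documents. The rise from 0.17 to 0.38 depends on an assumed 60% unaided pass rate, an assumed 25% look-up share, and certain success for those who look up.

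A reader might go further and conclude that objective 3 is biased upward as a fact, or that a pass would be invalid. The documents do not support that, since they give no evidence that any HCP will look answers up. This is a weakness of measurement worth correcting before fielding, not an error in the plan's arithmetic.

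**What to change.** 1. In the Q7 and Q8 stems, keep the SPC as the standard but add: *Please answer from your own knowledge, without consulting the SPC, the RM tools or the internet.* If the preamble already says this, repeat it at the stems.
2. Record page-level time for Q7 and Q8 and set an upper flag before fielding starts.
3. Report Knowledge success with and without flagged HCPs, as a descriptive sensitivity only.
4. In section 9.9.2, state that closed items do not prevent look-up, so the knowledge result may be an upper estimate.

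The cost is one line in two stems, a time stamp with a flag, one extra line in a results table, and one sentence of text. Sample size, endpoints and schedule do not change. Page timing not recorded during fielding cannot be recovered afterwards.

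There are limits. An instruction cannot enforce unaided answering. Slow timing is an imperfect marker and will also catch clinicians who are interrupted. The with/without comparison is unstable with 10 HCPs, and the reported knowledge figure may be slightly lower.

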The distribution of the responses to questions assessing all study objectives will be presented in the study report. It is to be noted that the selection of this threshold for success is subjective and not based on a priori knowledge, experience, or established scientific criteria in the education or risk communication or evaluation literature. Therefore, the results will be contextualized within the context of other available information.

The following will be reported as part of the analysis:

• Survey administration

- The number of HCPs by select medical specialty (ie, infectious disease physicians, pharmacists, as applicable).
- The number of survey invitations issued by strata (ie, by speciality).
- The number of survey invitations returned due to incorrect E-mail address of HCPs invited to participate in the survey.

• Demographic characteristics of participants

- Distribution of participants by region.
- Distribution by medical specialty.
- Distribution of participants by years in medical practice.
- Distribution of participants by number of patients treated with voriconazole in the past 12 months.
- HCP responses to questions pertaining to the survey objectives:

1. Awareness of the RM tools.

• The number and percentage of HCPs who acknowledged receiving each of the tools.

2. Utilization of the RM tools

- The number and percentage of HCPs indicating which tools they utilized when treating patients with voriconazole.
- The number and percentage of HCPs indicating they read tools.

3. HCP's knowledge/understanding of the risks

• The number and percentage of HCPs who correctly responded to each question/item about the risks of phototoxicity, SCC of the skin and hepatic toxicity with voriconazole.

4. HCPs' self-reported practices

• The number and proportion of HCPs whose responses to each behavior/practice related questions are consistent with the SPC¹ prescribing information.

Analysis of participation rate

The following different cases will be distinguished:

- HCPs who do not participate (R): HCPs who do not respond or that explicitly indicate their refusal to participate.
- HCPs with partially answered questionnaires (P): HCPs click on the link provided in the invitation email, and who begin answering the questionnaire but never submit it.
- Failed screening (F): HCPs who will not be eligible for the survey (HCPs who will not meet inclusion criteria and/or who will meet any of the exclusion criteria).

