10.3. Participant withdrawal

Any participant who will not complete all survey questions will be considered as withdrawal from the study.

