Not useful 17.2 HCP Checklist rograming Note: if response to Q11 or (Not Som useful us 17.3 Patient Alert	Somewhat useful Q12 is YES, the newhat	No opinion/not sure 	Very useful	Extremely useful
useful 17.2 HCP Checklist rograming Note: if response to Q11 or Q Not Som useful us 17.3 Patient Alert	useful Q12 is YES, the newhat	opinion/not sure	useful	useful
rograming Note: if response to Q11 or	Q12 is YES, the	hey can continu		
Not Som useful us	iewhat]		ie with Q	17.3
useful us 17.3 Patient Alert		NI. X7		
	-	No Ver nion/not usef sure	•	remely seful
Which precautionary measures d prescribe VFEND (voriconazole))? Please check			or whom you
Avoiding exposure to dire		taviaity		
Detecting signs and symptUse with caution in patien	•	•	testinal u	lceration or
diverticulitis	•	•		
Dermatologic evaluation s basis	hould be perfo	formed on a syst	tematic ar	nd regular

	Covering sun exposed areas of skin		
	Use sufficient sunscreen with high sun protect	ion factor (SPF)	
	Clinical signs of liver damage, such as jaundic doctor immediately	e that warrant con	tacting the
	International Normalized Ratio regular monitor	oring	
	Avoid invasive dental procedures		
	Note: if response to Q11 or Q12 is YES, they can tents of the Patient Alert Card" in Q18a	n continue with op	otions
18a.	Do you, or another member of your healthcar other) perform each of these activities when it VFEND (voriconazole)? (Please check one rebelow).	nitiating treatment	with
		Yes	No
	Discuss contents of the Patient Alert Card		
	Advise patient to avoid exposure to direct sunlight and/or to use measures such as protective clothing and sunscreen		
	Discuss risk of lymphoma		
	Discuss risk of gastric perforation		
	Advise patient of importance of monitoring risks of VFEND (voriconazole) use and signs and symptoms of serious risks that warrant contacting doctor immediately		
	Discuss risk of amyloidosis		
19. How	frequently do you perform Liver Function Tests	s (specifically AST	T, ALT)?
	At VFEND (voriconazole) treatment initiation month	and weekly therea	after for one
	At every contact		
	Monthly		

		Other [Free text] I do not know
20.	of VI	ere are no changes in Liver Function Tests (LFTs) after one month of initiation FEND (voriconazole), how often do you monitor liver function during VFEND ment maintenance?
		Weekly
		Monthly
		Other [Free text]
		I do not know

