21.		often do you perform a dermatologic evaluation when VFEND (voriconazole) ntinuously used despite the occurrence of phototoxicity-related lesions? Weekly Monthly Every two months
		On systemic and regular basis
		I do not know
22.		which of below condition(s) would you discontinue VFEND (voriconazole) in a nt? (Select the one best response).
		Phototoxicity
		Squamous Cell Carcinoma (SCC)
		Premalignant lesions
		All of the above

23. Did you or another staff member request additional copies of the VFEND (voriconazole) RM tools?

Redacted

Voriconazole A1501110 NON Version 1.0, 16	-INTERVENTIONAL STUDY PROTOCOL August 2024
	Yes
	No
[CLOSING	
	Thank you.

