Knowledge about the RM tools	Q7. According to the SPC/PI, the known risks for VFEND (voriconazole) are as follows: (Please select only one response for each of the risks listed in the table below.) Q8. Please select only one response for each statement about VFEND	Yes	Question completed correctly (6 points) Question completed correctly (5 points)	An HCP is considered successful for Knowledge when he/she provides at least 9 out of 11 (~80%) correct/desirable responses. Success for
Self-declared behavior/ Practice	(voriconazole) below: Q18. Which precautionary measures do you communicate to your patients for whom you	Yes	Question completed desirably (6 points)	Knowledge: if ≥80% of HCPs are successful An HCP is considered successful for awareness when he/she provides
	prescribe VFEND (voriconazole)? Please check all that apply. 18.a Do you, or another member of your healthcare team (e.g., nurse, pharmacist or other) perform each of these activities when initiating treatment with VFEND (voriconazole)? (Please check one response for each activity below).	Yes	Question completed desirably (6 points)	desirable responses to all sub-questions. Success for self-reported practices if ≥80% of HCPs are successful
	Q19. How frequently do you perform Liver Function Tests (specifically AST, ALT)?	Yes	Question completed desirably (Answer 1 is desirable)	

Q20. If there are no changes in Liver Function Tests (LFTs) after one month of initiation of VFEND (voriconazole), how often do you monitor liver function during VFEND treatment maintenance?	Yes	Question completed desirably (Answer 2 is desirable)	
Q21. How often do you perform a dermatologic evaluation when VFEND (voriconazole) is continuously used despite the occurrence of phototoxicity related lesions?	Yes	Question completed desirably (Answer 4 is desirable)	
Q22. For which of below condition(s) would you discontinue VFEND (voriconazole) in a patient? (Select the one best response).	Yes	Question completed desirably (Answer 4 is desirable)	

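### Every question is mandatory, but Q18 has no 'None of these' and Q22 has no 'None of these' or 'I do not know', so some HCPs must guess or break off; this can raise the Q22 result and distort the Q18 counts

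*Protocol*

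**What the plan says.** **Mandatory answering.** Protocol section 9.9.2: "All questions must be answered in order to complete the survey". The opening of the Annex 1.2 questionnaire repeats it: "Please provide a response to all questions and statements".

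**Incomplete surveys.** Section 10.3: "Any participant who will not complete all survey questions will be considered as withdrawal from the study". Section 9.7 keeps a separate category P for HCPs "who begin answering the questionnaire but never submit it", apart from completers (C). Sections 9.1 and 9.5 keep the survey open until 10 completed surveys are in, or until the 60 to 90 day window closes.

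**Q18.** The stem ends "prescribe VFEND (voriconazole)? Please check all that apply". Nine measures follow, the last being "Avoid invasive dental procedures". There is no option for an HCP who communicates none of them. Annex 1.5 gives the question 6 points.

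**Q22.** The instruction is "Select the one best response". The options are phototoxicity, SCC, premalignant lesions, and 'All of the above'. Annex 1.5 credits only the fourth. There is no 'none' and no 'I do not know'.

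**Neighbouring items.** Q7, Q8, Q19, Q20 and Q21 each offer a don't-know answer. Q18a is yes/no for each activity, so a truthful 'No' is available.

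**Scoring and reporting.** Under Annex 1.5 an HCP succeeds on self-declared practice only with desirable responses to every sub-question, and the objective succeeds if at least 80% of HCPs do. Section 9.7 also reports the number and proportion for each practice question separately.

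**The concern.** Two scored practice questions combine a compulsory answer with a list that leaves some respondents no truthful choice. At Q18 this is the HCP who counsels on none of the nine measures. At Q22 it is the HCP who does not know, or who would not stop treatment for any of the listed conditions. Such an HCP can give an untrue answer or abandon the survey.

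An untrue answer puts error into a result that is reported on its own. At Q22 one of the four available answers is the credited one, so guessing can only add credit that is not earned. At Q18 the answer pattern of most interest to a risk-minimisation survey, that nothing was communicated, cannot be recorded. Break-off has a different effect: it may remove an unsuccessful HCP from the denominator. With about 10 completed surveys, one HCP is worth 10 percentage points. No later analysis can recover an answer the instrument did not allow.

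**Working it through.** The protocol gives no figure to reproduce here: the sample size of 10 is described as empirical, and no guessing or break-off rate is stated. The inputs from the documents are the option lists (Annex 1.2), the scoring rule (Annex 1.5), the target of 10 completed surveys (section 9.5) and the 80% mark, which is 8 of 10. The true number correct, random guessing and the number of break-offs are my assumptions, shown as ranges. Annex 1.5 sets the 80% mark for the objective, so for Q22 alone 8/10 is only a yardstick.

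**1. Q22 reported on its own.** Let t of 10 HCPs truly give the credited answer and w others guess at random among four options.

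Expected result = (t + w/4)/10.

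For t = 7, reaching 8/10 needs at least one lucky guess: P = 1 − 0.75^w.

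| t | w | Expected result | P(at least 8/10) |
|---|---|---|---|
| 7 | 1 | 72.5% | 0.25 |
| 7 | 2 | 75.0% | 0.44 |
| 7 | 3 | 77.5% | 0.58 |
| 6 | 2 | 65.0% | 0.06 |
| 6 | 3 | 67.5% | 0.16 |

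For t = 6, two lucky guesses are needed. With w = 3: 3 × 0.25² × 0.75 + 0.25³ = 0.141 + 0.016 = 0.16. With the missing options in place and scored as not desirable, the result is t/10 (70% or 60%) and cannot reach 8/10 by this route.

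**2. Q18 option counts.** Six points imply that six of the nine measures are desirable and three are distractors. One random tick by an HCP who communicates none lands on a desirable measure with probability 6/9 = 67%. It adds a false count there, or otherwise to a distractor.

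**3. Objective 4 at HCP level, everyone finishing.**
- A single forced tick at Q18 cannot earn 6 points. The HCP fails, exactly as with 'None of these'.
- A lucky answer at Q22 changes the outcome only for an HCP who already has desirable answers to Q18, Q18a, Q19, Q20 and Q21. For that HCP a random guess turns failure into success with probability 1/4. If 7 of 10 pass and one more has Q22 as the sole gap, the expected result is 7.25/10 = 72.5%, and the chance of 8/10 is 0.25.

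**4. Objective 4 at HCP level, with break-off (illustration only).** Suppose 7 of 10 starters would pass and only failing HCPs leave:
- no break-off: 7/10 = 70%
- one: 7/9 = 77.8%
- two: 7/8 = 87.5%, above the 80% mark.

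If leavers are instead replaced until there are 10 completers, a true pass rate of 0.70 with a share b of starters lost (all failing) becomes 0.70/(1 − b) among completers. For b = 0, 5%, 10% and 20% this gives 0.70, 0.74, 0.78 and 0.875, and the binomial chance of at least 8/10 is 0.38, 0.49, 0.61 and 0.88.

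**The case against.** A reader might infer that the missing options inflate objective 4, because the HCPs with the weakest practice are either credited falsely or dropped. The documents do not support that in general.

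- **Scoring.** The all-sub-questions rule absorbs most forced answers. An HCP with weak practice throughout fails whatever is ticked at Q18 or Q22. This stands. The one gap is the HCP whose sole failing is Q22.
- **Break-off.** No passage gives a break-off rate or links leaving to these two items. This stands, and the figures in step 4 are illustrations.
- **Exclusion.** Section 10.3 speaks of withdrawal but does not say how partial answers are analysed, and section 9.7 counts P in the response-rate denominator, so break-offs are not hidden. Exclusion is an inference from section 10.3, the split between C and P, the target of completed surveys, and section 9.6.1, which asks for a completed data collection tool for every included participant. It is a reasonable inference, but not a stated rule.
- **Direction.** The Checklist shown in Annex 1.2 words discontinuation differently for phototoxicity than for premalignant lesions and SCC, whereas the Q22 key credits only the answer that treats all three alike. An HCP who follows the Checklist wording may be scored as failing, which would push the result down. So the net direction for objective 4 is not established. Those passages need to be reconciled in their own right.
- **Safeguards.** Section 9.9.1 plans a test for clarity and for suggestive questions, and section 9.9.2 plans user acceptance testing. Either could catch the gap, but neither commits to adding the options.
- **Stakes.** The 80% mark is described as subjective and is not formally tested. This limits the consequence but does not make a forced guess informative.

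**Conclusion.** The point holds in a limited form and is minor. Certain from the text: every question is compulsory, Q18 has no 'none', and Q22 has no 'none' or 'I do not know', unlike Q19 to Q21. It follows that Q18 cannot record an HCP who communicates no measure, that forced ticks add false counts, and that guessing can lift the separately reported Q22 result. With 7 of 10 truly correct and one to three random guessers, the expected lift is 2.5 to 7.5 percentage points, and the chance of reaching 8/10 is 0.25 to 0.58. These sizes rest on random guessing and on the assumed number of guessers.

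For the HCP-level result of objective 4, inflation is possible but not shown. It needs an HCP whose only gap is Q22 and who guesses right, or failing HCPs who break off and are left out of the analysis.

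**What to change.** Before the survey is programmed:

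1. Add 'None of these' to Q18 as an exclusive option that cannot be combined with any other tick.
2. Add 'None of these' and 'I do not know' to Q22, in line with Q19 to Q21.
3. State in Annex 1.5 that these answers are scored as not desirable.
4. Add to section 9.7 a count of category P by last question answered, so that any clustering of break-offs at Q18 or Q22 is visible.

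The mandatory-answer setting can stay, since every respondent to these two items who counsels on nothing, does not know or would stop for none of the conditions will then have a truthful choice. The cost is three response options, one scoring line and one line of reporting. The observed practice score may be slightly lower.
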